#### Prior derivation

For the current study, data from the pre-clinical animal studies were available. Therefore, the following prior will be used: A combination of the observed toxicity data from a study in rats further supported by data from a study in dogs.

#### Prior from rat data:

Based on the IMPD, the starting dose of CB-103 will be 15 mg, which is expected to achieve an exposure ( $\text{AUC}_{0-24}$ ) in humans of approximately 600  $\mu\text{g} \cdot \text{h}/\text{mL}$ . This exposure is comparable with 1/10th of the exposure at the HNSTD (30 mg/kg/day) in male rats. It is therefore highly unlikely that a DLT would occur at this dose, leading to the prior

assumption that the median DLT rate at 15 mg is 0.1%. On the other hand, assuming dose-proportionality in humans, a dose of 150 mg would approximately have an exposure of 6000  $\mu\text{g}\cdot\text{h}/\text{mL}$ , i.e., the same as the exposure at the HNSTD in rats. Using a cautious approach, the median DLT rate at  $d^* = 150$  mg was therefore assumed 25%.

#### Prior from dog data:

Based on the IMPD, the exposure at  $1/10^{\text{th}}$  of the HNSTD (8.6 mg/kg/day) in (male) dogs is approximately 9000  $\mu\text{g}\cdot\text{h}/\text{mL}$ , which we assume would correspond to a human dose of  $15 \cdot 9000 / 600 = 225$  mg. A cautious approach was chosen again, using a median 25% DLT rate at  $d = 225$  mg.

**Table 19** Summary of prior distribution

Prior Component	Mixture Weight	Mean vector	STD vector	Correlation
1: Rat	0.500	-1.122, 0.299	1.98476, 0.9906	-0.0004715777
2: Dog	0.500	-1.682, -0.101	1.9847620 0.9906	-0.0004715777

A summary of the prior probabilities of DLT at different doses, as well as the corresponding probability of under-, targeted and overdosing, are shown in Table 20. Graphically, the prior medians with accompanying 95% credible intervals are shown in Figure 6. As can be seen from both Table 20 and Figure 6, the prior medians of the DLT probabilities are in line with the prior medians derived from the two animal studies, and the uncertainty around the medians is large, showing the low amount of in-men information this prior provides.

[figure not shown]
**Table 20** Prior probabilities of DLT at selected doses

Dose	Probability of true DLT rate in			Mean	STD *	Quantiles		
	[0–0.16)	[0.16–0.33)	[0.33–1]			2.5%	50%	97.5%
10 mg	0.857	0.069	0.075	0.077	0.162	0	0.008	0.647
15 mg	0.832	0.079	0.089	0.089	0.173	0	0.012	0.685
30 mg	0.775	0.101	0.123	0.118	0.197	0	0.025	0.757
60 mg	0.688	0.129	0.182	0.165	0.228	0	0.057	0.828
120 mg	0.524	0.178	0.298	0.253	0.266	0.003	0.144	0.898
180 mg	0.384	0.186	0.429	0.347	0.3	0.006	0.256	0.954
240 mg	0.31	0.171	0.519	0.418	0.324	0.008	0.352	0.986
320 mg	0.26	0.153	0.588	0.479	0.339	0.011	0.449	0.998
400 mg	0.229	0.141	0.63	0.52	0.345	0.013	0.525	0.999

Doses printed in bold type meet the overdose criterion,  $P(\text{overdose}) < 0.25$ .

\* STD = standard deviation.

**Figure 6** Prior medians and 95% credible intervals.

The MTD may be considered reached if one of the following criteria is fulfilled:

1. The posterior probability of the true DLT rate in the target interval (16%-33%) of the MTD above 50%

OR

2. At least 6 patients have been treated at MTD, including the MTD/RP2D confirmatory cohort

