### **7.4.3 Criteria for Dose Escalation and Determination of the Maximum Tolerated Dose**

#### **Phase I, Part A – Escalation**

##### **Definition of MTD and RP2D**

For any given schedule, the MTD is the highest dose of CB-103 if the following criteria are fulfilled: the posterior probability of the true DLT rate in the target interval [0.16 – 0.33] of the MTD is above 0.50 and 6 patients have been treated at the MTD/RP2D confirmatory cohort of the treated patients in the first 28 days of CB-103 treatment under that schedule. If the MTD cannot be reached in the dose escalation part of the study and the therapeutic dose range of CB-103 with the IC50 being reached, the RP2D will be determined at a dose below or equal to the MTD, based on the PD, PK, safety and potential efficacy data, upon review of all study data by the CRC and Sponsor. Adverse events and laboratory abnormalities considered to be DLTs are defined in Section 7.4.4 on DLT Assessments.

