## 10. STATISTICAL CONSIDERATIONS AND ANALYSIS PLAN

Detailed methodology for summary and statistical analyses of the data collected in this study will be documented in a Statistical Analysis Plan (SAP) covering Part A and Part B of this study. The SAP will provide all data handling rules, including the management of missing values and the handling of data for withdrawn patients. The SAP will also outline protocol deviation criteria. Any deviations from the planned analyses specified or populations defined within the SAP will be justified in writing and presented within the final clinical study report (CSR) for Part A and for Part B.

The clinical database locks, for Part A and Part B respectively, will occur after all data for the respective part of the study are reconciled (i.e., “cleaned”) for all patients who participate in the dose escalation Part A for the Part A CSR and in the expansion Part B at the MTD/RP2D for the Part B CSR. Two CSRs will be generated for this study, one for Part A (dose escalation) and one for Part B (dose expansion). The SAPs for each part of the study will be finalised and signed before the database lock.

In all tables, listings and figures of Part A, the dose-escalating cohorts will be reported from the lowest to the highest dose. In the Part B of the study expansion arms will be reported by indication. Where appropriate, for efficacy assessment, in addition those patients analysed by “NOTCH+” status who received what becomes identified as the MTD/RP2D during Part A and B, will be combined and summarised under the same dose level.

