#### **10.5.1.2 Dose-Finding of Single Agent CB-103**

A 2-parameter BLRM (Neuenschwander et al., 2008) will be used for dose escalation. Standardised doses will be used such that one of the doses ( $d^*$ ) equals 1, e.g., doses are rescaled as  $d/d^*$ . As a consequence,  $\alpha$  is equal to the odds of the probability of toxicity at  $d^*$ . All information currently available about the dose-DLT relationship of CB-103 is summarised in a prior distribution. For this study, this includes pre-clinical data about the starting dose and predicted MTD of CB-103 within different animal species. This prior distribution is then updated after each cohort of patients with all of the DLT data available in the DDS from the current trial. Once updated, the distribution summarises the probability that the true rate of DLT for each dose lies in the following categories:

- [0,16%) under-dosing
- [16%,33%) targeted toxicity
- [33%,100%] excessive toxicity

The EWOC principle (Babb et al., 1998, Neuenschwander et al., 2008) mandates that any dose of CB-103 that has more than a 25% chance of being in the excessive toxicity category is not considered for the next dose cohort. After a clinical synthesis of the available toxicity information (including adverse events that are not DLTs), PK, PD, and efficacy information as well as the recommendations from the Bayesian model, the CRC will determine the dose regimen for the next cohort at a dose-escalation teleconference. In case that another regimen is evaluated during the study, a separate 2-parameter logistic regression will be used for the assessment of the respective DLT rates. However, all data that are available from the other regimen (or regimens) before "First Patient First Visit" (FPFV) for the new regimen has happened will be incorporated into an informative, meta-analytic predictive (Neuenschwander et al 2015) prior distribution. This prior distribution will be mixed with a weakly informative prior distribution to hedge against a potential prior-data conflict.

The frequency of DLTs will be tabulated by dose for patients in the dose escalation phase and information about the DLTs will be listed by dose.

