### 10.5.1.3 Bayesian Logistic Regression Model for MTD Determination

The objective of the design is to determine the MTD defined as the highest dose with less than 25% risk of the true DLT rate being above 33%. The Part A dose-finding will be guided by a Bayesian 2-parameter logistic regression model with overdose control. These designs have been shown to be superior regarding the precision of MTD determination compared to 3+3 designs and have been particularly endorsed by the FDA.

The model is formulated as follows:

$$\text{logit}(p(d)) = \log(\alpha) + \beta \cdot \log(d/d^*),$$

where  $\text{logit}(p) = \log(p/(1-p))$ .  $p(d)$  represents the probability of having a DLT in the first cycle at dose  $d$ ,  $d^* = 150$  mg is the reference dose, allowing for the interpretation of  $\alpha$  as the odds of a DLT at dose  $d^*$ , and  $\theta = (\log(\alpha), \log(\beta))$  with  $\alpha, \beta > 0$  is the parameter vector of the model.

Since a Bayesian approach is applied, a prior distribution  $\pi(\theta)$  for the unknown parameter vector  $\theta$  needs to be specified. This prior distribution will be specified as a mixture of two multivariate normal distribution, i.e.

$$\pi(\theta) = \varphi_1 \pi_1(\theta) + \varphi_2 \pi_2(\theta)$$

with

$$\varphi_i, i = 1, 2 \text{ the prior mixture weights } (\varphi_1 + \varphi_2 = 1)$$

and

$$\pi_i(\theta) = \text{MVN}(\mu_i, \Sigma_i)$$

the multivariate normal distribution of the  $i$ -th component with mean vector  $\mu_i$  and covariance matrix  $\Sigma_i$ , with

$$\Sigma_i = \begin{pmatrix} \sigma_{i,11}^2 & \sigma_{i,11}\sigma_{i,22}\rho_i \\ \sigma_{i,11}\sigma_{i,22}\rho_i & \sigma_{i,22}^2 \end{pmatrix}$$

Mixture prior distributions have the advantage that they allow for specification of different logistic dose-toxicity curves, therefore making the prior more robust.

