**Table 5 Prior probabilities of DLT at selected doses**

Dose	Probability of true DLT rate in			Mean	SD	Quantiles		
	[0–0.16)	[0.16–0.33)	[0.33–1]			2.5%	50%	97.5%
10 mg	0.857	0.069	0.075	0.077	0.162	0	0.008	0.647
15 mg	0.832	0.079	0.089	0.089	0.173	0	0.012	0.685
30 mg	0.775	0.101	0.123	0.118	0.197	0	0.025	0.757
60 mg	0.688	0.129	0.182	0.165	0.228	0	0.057	0.828
120 mg	0.524	0.178	0.298	0.253	0.266	0.003	0.144	0.898
180 mg	0.384	0.186	0.429	0.347	0.3	0.006	0.256	0.954
240 mg	0.31	0.171	0.519	0.418	0.324	0.008	0.352	0.986
320 mg	0.26	0.153	0.588	0.479	0.339	0.011	0.449	0.998
400 mg	0.229	0.141	0.63	0.52	0.345	0.013	0.525	0.999

Doses printed in bold type meet the overdose criterion,  $P(\text{overdose}) < 0.25$ .

The MTD may be considered reached if one of the following criteria is fulfilled:

1. The posterior probability of the true DLT rate in the target interval (16%-33%) of the MTD is above 50%

OR

2. At least 6 patients have been treated at MTD, including the confirmatory cohort.

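### Protocol 7.4.3 needs two conditions together before an MTD is declared; protocol 10.5.1.3 and the SAP accept either one

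*Protocol*

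**What the plan says.** Protocol 7.4.3, under the definition of MTD and RP2D, sets a joint rule for each schedule: "For any given schedule, the MTD is the highest dose of CB-103 if the following criteria are fulfilled". The criteria are that the posterior probability of a DLT rate in the target interval "of the MTD is above 0.50 and 6 patients have been treated at the MTD/RP2D confirmatory cohort".

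Protocol 10.5.1.3, after Table 20, sets an either-rule: "The MTD may be considered reached if one of the following criteria is fulfilled". The two criteria are the same posterior probability above 50% and at least 6 patients treated at the MTD, joined by a capitalised OR. SAP 5.6.1.2, after Table 5, repeats this, with the second criterion worded as "At least 6 patients have been treated at MTD, including the confirmatory cohort".

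Two further provisions do not depend on which rule applies. Protocol 10.5.1.3 has the MTD "defined as the highest dose with less than 25% risk of the true DLT rate being above 33" per cent. Under EWOC in 10.5.1.2, "any dose of CB-103 that has more than a 25% chance of being in the excessive toxicity category is not considered" for the next cohort.

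Protocol Appendix 10 and SAP Appendix 2 report 500 simulated trials for each of three toxicity scenarios: P (aligned with prior means), H (high toxicity) and LH (low, then high). Neither appendix names the declaration rule or the cohort size that was simulated.

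**The concern.** The joint rule and the either-rule are different decision rules for the primary objective of dose escalation. Version lag between the documents is not the explanation, because protocol version 4.3 contains both. SAP section 6 records no change from the analysis planned in the protocol, so the conflict is not acknowledged. If it stays, whether an MTD was reached could be settled by choosing the text after the data are seen.

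The wording of 7.4.3 adds a second problem. It places the 6 patients in the confirmatory cohort, yet section 5.1.1 opens that cohort only once the MTD/RP2D is defined. Read literally, the condition is circular.

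The published operating characteristics are also at issue. If Table 3 was not simulated under the joint rule, the rule in 7.4.3 has no published performance behind it.

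**Working it through.** **1. Rebuild the model and check it.** Inputs are from protocol 10.5.1.3 and Table 19: logit p(d) = log α + β·log(d/150). The prior on (log α, log β) is an equal mixture of normals with means (-1.122, 0.299) and (-1.682, -0.101), SDs 1.98476 and 0.9906, and correlation -0.0004715777. The posterior is proportional to the prior times the product over doses of p^x(1-p)^(n-x), integrated on a grid. Target is [0.16, 0.33) and overdose is 0.33 or more. This reproduces Table 20 within about 0.006 and Appendix 10 Table 1 within about 0.01.

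**2. A case where the rules disagree.** Data: 0/3 at 15, 30 and 60 mg, then 2/6 at 120 mg.

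- At 120 mg: P(under) 0.339, P(target) 0.437, P(over) 0.225.
- At the next dose, 180 mg: P(over) 0.574.

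The dose is admissible (0.225 < 0.25) and escalation is blocked (0.574 > 0.25), so 120 mg is the highest admissible dose. Six patients have been treated there, so the either-rule is met. P(target) is below 0.50, so 7.4.3 is not met.

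The same pattern (3 DLT-free patients per lower dose, then 2/6) splits the rules at 7 of 8 doses tested: 30, 60, 120, 240, 320, 400 and 600 mg, with P(target) 0.415-0.437. At 180 mg the dose is not admissible (P(over) 0.265).

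**3. The rules do not always disagree.** With 1/6 at a dose and 2/3 at the next one up, P(target) is 0.52-0.53 at 180-600 mg, so both rules are met. At 15-120 mg it is 0.41-0.46, so they split.

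**4. Which rule is behind Table 3?** The simulation was re-run from 15 mg on the Appendix 10 grid, with EWOC at 0.25, steps of at most 100% and a cap of 60 patients. Cohorts were of 3, or random 3-6. For the joint rule, the 6 were taken as patients treated at the dose. Joint-rule ranges cover all these settings and two conventions for when a dose counts as declared.

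| | P | H | LH |
|---|---|---|---|
| Mean patients, published | 19.13 | 15.30 | 19.89 |
| Mean patients, joint rule | 25.9-32.7 | 16.2-21.1 | 26.9-34.0 |
| Mean patients, either-rule, cohorts 3-6 | 19.3 | 13.8 | 19.9 |
| Mean DLTs, published | 3.09 | 3.68 | 3.25 |
| Mean DLTs, joint rule | 4.8-5.9 | 4.2-5.2 | 4.9-6.0 |
| Mean DLTs, either-rule, cohorts 3-6 | 3.2 | 3.4 | 3.3 |

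In P and LH the joint rule exceeds the published mean by at least 25.9 - 19.13 = 6.8 and 26.9 - 19.89 = 7.0 patients. No joint-rule trial ended with fewer than 2 DLTs, while Table 3 reports a minimum of 1. In H, mean patients do not separate the rules: the joint rule gets as close as 16.2.

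The either-rule is not established. With cohorts of 3-6 its H mean is 15.30 - 13.8 = 1.5 below the published value, about 7.5 standard errors at roughly 0.2 each. In H it selects a target dose in 67.0% of trials against 61.2% published. A further run of that setting gave maximum patients of 38 / 27 / 39 against 51 / 39 / 52. With cohorts of 3 the means are too low throughout (14.7 / 11.1 / 14.9).

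**5. Errata, in both documents.**

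- Table 3, scenario 3: 22.6 + 67.4 + 9.1 + 3.6 = 102.7%. Also 0.091 × 500 = 45.5, which is not a whole number of trials. If the other three entries are right, overdose is 100 - 22.6 - 67.4 - 3.6 = 6.4%.
- The text calls 150 mg the highest planned dose, chosen as MTD in 61.4% of scenario 1 trials. The simulated grid is 10, 15, 30, 60, 120, 180, 240, 320 and 400 mg, so 150 mg is not on it.
- The footnote to protocol Table 20 and SAP Table 5 says the bold doses meet P(overdose) < 0.25. The bold doses, 120-400 mg, have 0.298-0.63 and fail. The plain ones, 10-60 mg, have 0.075-0.182 and pass.

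**The case against.** The strongest case for leaving the plan alone is that little depends on the label. Protocol section 10 says "Detailed methodology for summary and statistical analyses of the data collected in this study will be documented in a Statistical Analysis Plan", and the SAP's rule is the either-rule, so the rule for the Part A report can be identified. That rule is permissive (may be considered), the Cohort Review Committee decides after clinical synthesis, and overdose control is identical under both rules. For once-daily dosing, section 2.5.6 reports 41 patients treated at 15-600 mg, one described DLT, no MTD reached and 600 mg as provisional RP2D. Nothing has been mislabelled.

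All of this stands, and it limits the weight of the point. It does not remove the contradiction. Section 7.4.3 applies per schedule, a twice-daily schedule is being explored, and the Part A report must say whether an MTD was reached.

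A reader might infer from the close means in P and LH that Table 3 was simulated under the either-rule. The documents do not support that. No rule is stated, scenario H and the maxima do not fit, and a hybrid rule written in neither document comes about as close: 6 patients plus either P(target) > 0.50 or about 15-18 patients in total gives 18-20 / 14-15 / 18-20 with cohorts of 3.

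A reader might also use these simulations to price the joint rule in extra patients. That is not supported either. It rests on one reading of the unclear 6-patient wording and on scenarios with true DLT rates of 0.35-0.63 at 180 mg, which the once-daily data have overtaken.

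**Conclusion.** The contradiction is real and visible in current text without any modelling. The rebuilt model shows that it affects plausible data, such as 2/6 at 120 mg after DLT-free lower doses. The consequence is confined to the MTD label in the Part A report and for any further schedule. It is not a safety failure and does not undermine the choice of 600 mg once daily.

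Table 3 is inconsistent with the joint rule in P and LH, on mean patients, mean DLTs and minimum DLTs, but it does not show which rule was used. That inference assumes EWOC at 0.25, the 100% step limit, cohorts of 3 or 3-6, and the 6 counted as patients treated at the dose.

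The posterior figures use the once-daily prior. For another regimen, "a separate 2-parameter logistic regression will be used for the assessment of the respective DLT rates" with its own prior, so they do not carry over to twice-daily dosing. The three errata stand on arithmetic or the printed tables alone and do not depend on the rule conflict. This should be fixed.

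**What to change.** Reword protocol 7.4.3 to the either-rule of 10.5.1.3 and SAP 5.6.1.2, in identical words in all three places. Keep the condition of less than 25% risk of overdose. State whether the 6 are DLT-evaluable patients at the dose or patients in the confirmatory cohort. If the sponsor prefers the joint rule, 10.5.1.3 and the SAP must change instead and Table 3 must be re-run under it.

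The sponsor should state in Appendix 10 and SAP Appendix 2 which declaration rule and cohort sizes Table 3 simulated.

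In both documents, correct or re-run the scenario 3 row, delete or correct the sentence giving 150 mg as MTD in 61.4% of trials, and reverse the bold legend of Table 20 / SAP Table 5.

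With the either-rule the cost is one reworded passage, a clarification of the simulation settings and errata in two documents, with no extra patients.

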### Statistical model assessment

The single agent model was assessed using two different metrics:

1. Hypothetical data scenarios: for various potential data constellations as they could occur in the actual trial, the maximal next doses as allowed by the model and by the 100% escalation limit are investigated. Data scenarios thus provide a way to assess the “on-study” behaviour of the model.
2. Simulated operating characteristics: these illustrate for different assumed true dose-toxicity relationships, how often a correct dose would be declared as MTD by the model. They are a way to assess the “long-run” behaviour of the model.

In summary, the model showed very good behaviour as assessed by these metrics. More details can be found in [Appendix 10](#).

### 10.5.2 Part B (Expansion)

Once the MTD/RP2D is determined, enrolment into Part B (expansion) can be started by enrolling patients into several expansion arms for selected cancer indications. All patients in Part B will need to have tumours characterised by alterations and over-activation of the NOTCH signalling pathway (mutations, translocations, over-expressions).

For the primary analysis of the expansion arms a Bayesian hierarchical exchangeable binomial design will be used. The assumption of the model is that the true response rate in each of the preliminary indications for the Part B expansion arms is fully exchangeable.

For these indications the response criteria for success is a point estimate (from the model) above 25%.

The T-ALL/T-LBL indications are assumed to be only partially exchangeable with other indications. The success criteria for this indication is a point estimate (from the model) above 40%.

A robust hierarchical model (Neuenschwander et al., 2015) will be used for the analysis of the response rate  $p_k$  in the different indications  $k = 1, \dots, K$ . The number of responders in each indication follows a binomial likelihood function. For exchangeable indications ( $k = 1, \dots, K - 1$ ) it is assumed that

$$\text{logit}(p_k) \sim N(\mu, \tau^2)$$

On the other hand, for the partially (or non-) exchangeable indication  $K$  we use the mixture

$$\text{logit}(p_K) \sim N(\mu, \tau^2) \text{ with probability } \pi,$$

$$\text{logit}(p_K) \sim N(m, s^2) \text{ with probability } 1 - \pi$$

setting  $m = \text{logit}(0.3)$  and  $s = 2.2$ .

Further, the following weakly informative priors (Friede et al., 2016; Friede et al., 2017) are used:

$$\mu \sim N(\text{logit}(0.2), 2.5^2)$$

$$\tau \sim HN(1)$$

For these exchangeable indications, the advantage of this model is the fact that borrowing information across indications improves the precision of the estimators of the response rate. On the other hand, for the possibly different indication, the mixture approach hedges for a too-optimistic assumption about similarity. Therefore, the described approach captures the design adequately.

Other characterisations of the posterior distribution will be evaluated as appropriate. The final analysis will take place after the last expansion arm was closed for futility or the last patient of the last expansion arm had the final end-of-study visit.

## 10.6 SECONDARY ANALYSES

The following sections describe the secondary analyses that will be performed for Part A (escalation) & Part B (expansion) of this study.

## **10.6.1 Safety Analyses**

### **10.6.1.1 Adverse Events**

The Medical Dictionary for Regulatory Activities (MedDRA) coding dictionary will be applied for the coding of AEs. NCI-CTCAE toxicity Grades will be utilised for classifying severity.

Adverse events, related adverse events, serious adverse events and related serious adverse events, adverse events with NCI CTCAE Grades  $\geq 3$ , related adverse events with NCI CTCAE Grades  $\geq 3$ , adverse events leading to premature discontinuation, interruptions or discontinuation of study drug or dose modification will be analysed descriptively utilising corresponding MedDRA System Organ Classes (SOCs) and Preferred Terms (PTs).

Deaths within 28 days after the last dose and the corresponding reasons will be summarised. Also, all deaths overall will be summarised.

